4.3 REGISTRATION AND RANDOMIZATION/BLINDING

Subjects who have signed an informed consent will be registered and receive a unique subject identifier. Subjects must be registered in the IRT system prior to dispensing any drug to the participant. Subjects enrolled to the Phase 3 randomized stage of the study will be randomized in the IRT system. Treatment arm will be assigned by the IRT system. Once randomized, subjects should start study treatment within 7 days of randomization. Further details about the subject registration and randomization process are available in the IRT Manual.

4.4 STUDY SITES

This study may be conducted in approximately 125 centers. Enrollment is expected to take approximately 24 months.

4.5 DISCONTINUATION FROM STUDY

Discontinuation from study treatment (discontinuation of all study drugs) and discontinuation from the study might be linked or might be separate events, depending on the triggering action, decision or outcome. Subjects will be discontinued from study treatment for any of the following reasons:

- Disease progression
- Intolerable toxicity (all study drugs discontinued)
- Subject requests to withdraw consent for treatment
- Pregnancy
- Initiation of therapeutic intervention not permitted by the protocol
- Investigator discretion
- Discontinuation of the study by the Sponsor

Subjects will continue to be followed for PFS and/or OS per the schedule of assessments.

Subjects who discontinue from study treatment will continue to be followed for AEs and other protocol required procedures as per the study assessment table.

All subjects who have CTCAE Grade 3 or 4 laboratory abnormalities at the time of withdrawal should be followed until the laboratory values have returned to Grade 1 or 2, unless in the opinion of the Investigator, it is not likely that these values are to improve because of the underlying disease. In this case, the Investigator must record his or her reasoning for making this decision in the subject's medical records and as a comment on the eCRF.

U2-VEN-207

5 STUDY ASSESSMENT AND TREATMENT SCHEDULE (PHASE 2)

The table below lists all the required assessments that should be performed at each study visit for subjects enrolled to the Phase 2 stage of the trial.

TABLE 4: STUDY ASSESSMENT AND TREATMENT SCHEDULE

Cycle = 28 days	Screening ¹		Cycle 1 ²	112		Cycles 2-3 ³		Cycle 4³	43		Cycles (5-63	Cycles 9- 24 ⁴		EOT	30 and 90 day Safety FU ⁵	LTFU6	E0S7
Procedure/Days	D-30 to D0	D1	D2	D8	D15	D1	D1	D8 D	D15 I	D22	D1	D1 Q3 Cycles	D1 Q6 Cycles				
Medical history	×																
Rai staging	X						-	-									
ECOG performance status	X	X				X	×				×	X	X	X			X
Physical examination	X	X				X	×				X	X	X	X			X
Weight	×	×				×	×				×	×	×				
Vital signs ⁸	X	×	×	×		×	×				×	×	×	×			X
Hematology ⁹	X	X	X	×	X	X	×				×	X	X	X			X
Chemistry, LDH, Mg, Phos, Uric acid9,10	X	X	X	X	X	X		X11	×	X	X	X	X	X			X
PT/INR12	×																
HBV/HCV serology, Coombs test, CMV13	×																
CMV screening ¹⁴							×				X	X	X				
Quant IgG, IgA, IgM	X											X15					
β ₂ -microglobulin	×																
Serum pregnancy test ¹⁶	×																

Screening labs (hematology and chemistry only) must be conducted within 14 days prior to Cycle 1 Day 1. Patients must continue to meet eligibility criteria in respect to adequate organ system function as per Inclusion Criteria # 2 within the required screening timeframe, and importantly, on Cycle 1 Day 1. Hematology and chemistry results must be reviewed prior to dosing on Cycle 1 Day 1 to ensure subjects meet Inclusion #2 as per

10 See Section 8.5.3: Guidelines for Administration of Venetoclax for dose ramp-up schedule and recommended blood chemistry monitoring based on tumor burden.

² Study visits have a ± 1 day window

³ Study visits have a ±3 day window

 $^{^{4}}$ Study visits have a \pm 7 day window.

⁵ A 30-day (± 7 days) and a 90-day (± 7 days) safety follow up visit is required after the last dose of study drug. See Section 12.2.3 Adverse Event/Serious Adverse Event Recording. and/or death occurred in eCRF.

r End of Study (EOS) visit to be completed for subjects who are coming off study. Tumor Assessment should be performed if not done within previous 3 months. EOT and EOS may be the same visit if subject is discontinuing the study drugs and is not going into LTFU.

⁸ Heart rate, blood pressure, temperature, respirations.

⁹ Hematology and chemistry must be done prior to ublituximab administration.

¹¹ Cycle 4, day 8, 15 and 22 only required for patients receiving venetoclax and during the venetoclax ramp up.

¹² PT/INR to be done at screening and as clinically indicated. INR should be monitored closely in subjects receiving venetoclax and warfarin.

¹³ Serum virology to include HBSAg, HB cantibody, HCV AB, CMV IgG and CMV IgM or CMV by PCR if institutions SOC. If HBc antibody, HCV AB or CMV IgM or IgG is positive, subjects must be evaluated for the presence of 14 CMV screening by PCR for all subjects while receiving umbralisib approximately Q3 months beginning C4D1, C6D1, C9D1 and approximately every 3 months up to Cycle 24, and Q6 months thereafter. If CMV IgM or IgG active HBV, HCV, or CMV by PCR.

is positive, subjects must be evaluated for the presence of active CMV by PCR.

15 To be completed at screening, during Cycle 12, and during Cycle 24 only.

16 For females of childbearing potential, completed within 3 days prior to Day 1 of Cycle 1.

Dated: 05 October 2021 (Ver 4.0) U2-VEN-207

Cycle = 28 days	Screening ¹		Cycle 1 ²	e 12		Cycles 2-33		Cycle 43	e 43		Cycles 5-6³	Cycles Cycles 9- 5-6 ³ 24 ⁴	Cycles 30+4	EOT	30 and 90 day Safety FU ⁵	LTFU6	EOS7
Procedure/Days	D-30 to D0	D1	D2	D8	D15	D1	D1	1 80	D15	D22	D1	D1 Q3 Cycles	D1 Q6 Cycles				
BM biopsy/aspirate ¹⁷	X																
CLL mutation panel 18	Х							_	_								
EKG	×																
T/B/NK Cell Subsets ²⁰	X						X					X					
TLS risk-assessment ²¹	X						×	-									
Response assessment ²²	X						×					×	×			×	X
MRD (NeoGenomics)											X23	X	X			×	
AE Assessment	X	X	X	X	X	X	X	X	X	X	X	X	X	X	X		
Con Med Assessment		X	X	×	×	X	X				X	X	X	X			
Ublituximab ²⁴		×	×	×	×	×	×				×						
Umbralisib						Orally	r once d	aily wi	Orally once daily with food25	35							
Venetoclax ²⁶							J	Orally d	laily *se	Orally daily *see ramp-up schedule	pays di	ule					

26 Subject should have prior authorization for access to commercially available venetoclax.

¹⁷ Baseline BM within 90 days of C1D1. A post-baseline BM biopsy is required to confirm potential CR and for MRD testing.
18 For del(13q), del(11q), del(17p), and trisomy 12, IgHV and 7P53 gene mutation status in peripheral blood. This may be done within 60 days prior to C1D1. If IgHV status already documented in medical record it does

See lab manual for sample collection procedures.

²⁰ To be drawn pre-dose C1D1, during Cycle 4, Cycle 12, and approximately every 6 cycles thereafter until Cycle 24. Subjects that end treatment prior to Cycle 24 should continue to have T/B/NK collected until month 24.

²¹ TLS risk assessment according to Section 8.5.3.1 at baseline and on Day 1 of Cycle 4, prior to first dose of venetoclax.

²² Response assessment at baseline (within 30 days prior to Cycle 1 Day 1), and within 14 days prior to Cycles 4 & 12, and at least every 12 cycles thereafter. Radiologic assessment should include CT with contrast or MRI imaging of neck, chest, abdomen, and pelvis. A post-baseline BM biopsy is required to confirm potential CR.

²³ MRD at Cycle 6 for all subjects without signs of clinical progression, perform MRD testing by PB; repeat every 6 cycles. At Cycle 12, MRD by PB will be performed. Subjects in a ≥PR and who are MRD negative by PB, perform MRD testing in BM (central lab). If MRD BM positive, repeat MRD by BM (central lab) is required. Any subject in a CR before Cycle 12 who are MRD negative by PB, perform MRD testing in BM (central lab). If MRD BM positive, repeat MRD by PB should continue every 6 cycles. Subjects that end treatment prior to Cycle 24 should continue to have MRD collected through cycle.

²⁴ and every 6 cycles thereafter in LTFU. See laboratory manual for collection, processing and shipment instructions. 24 Ublituximab to be administered C1 D1, 2, 8 & 15, then D1 C2-6. After C6 no further ublituximab will be administered. 25 See Section 8.0 Treatment Plan for details on umbralisib administration based on treatment status and MRD status.

U2-VEN-207

6 STUDY ASSESSMENT AND TREATMENT SCHEDULE (PHASE

The table below lists all of the required assessments that should be performed at each study visit for subjects enrolled to the Phase 3 stage of the trial (version 3.0+).

TABLE 5: STUDY ASSESSMENT AND TREATMENT SCHEDULE

							_										
EOS,8				×			X			X	X	×					
LTFU7																	
30-and 90-Day Safety FU ⁶																	
ЕОТ				×			X			X	X	X					
Cycle 18 and Q3 Cycle ⁵	D1			X			X		X	X	X	×					X
Cycles 9, 12, 15 ⁵	D1			×			X		X	X	X	×					X
Cycles 5&6³	D1			X			Х		X	X	X	X					X
	D22									X		×					
Cycle 4 ⁴	D15									X		×					
Cyc	D8									X		X12					
	D1			X			X		X	X	X	X11					X
Cycles 2-3³	D1			X			X		X	X	X	×					
	D15									X	X	X					
Cycle 1 ²	D8									X	X	×					
Cy	D2									X	X	X					
	D1			×			X		X	X	X	×					
Screening ¹	D-30 to D0	X	X	X			X		X	X	X	X			X	X	X
Cycle = 28 days	Procedure/Days	Medical history	Rai Staging	ECOG	Performance	Status	Physical	Examination	Weight	Vital signs ⁹	Hematology ¹⁰	Chemistry, LDH,	Mg, Phos, Uric	acid10	PT/INR13	Hep B/C14	CMV15

Screening labs (hematology and chemistry only) must be conducted within 14 days prior to Cycle 1 Day 1. Patients must continue to meet eligibility criteria in respect to adequate organ system function as per Inclusion Criteria # 2 within the required screening timeframe, and importantly, on Cycle 1 Day 1. Hematology and chemistry results must be reviewed prior to dosing on Cycle 1 Day 1 to ensure subjects meet Inclusion #2 as per

² Study visits have a ±1 day window.

³ Study visits have a ±3 day window.

[·] Cycle 4 Day 8, 15, and 22 visits only for subject randomized to Arm A (U2-V). Study visits have a±3 day window.

⁵ Study visits have a ± 7 day window.

^{&#}x27;Subjects who discontinue from study treatment (for reasons other than progressive disease) will continue to be followed for progression until a non-protocol line of therapy is initiated. LTFU for PD and OS should be s A 30-day (± 7 days) and a 90-day (± 7 days) safety follow up visit is required after the last dose of study drug. See Section 12.2.3 Adverse Event/Serious Adverse Event Recording. entered approximately every 6 months. Enter date of disease progression and/or death occurred in eCRF.

Bind of Study (EOS) visit to be completed for subjects who are coming off study. Tumor Assessment should be performed if not done within previous 3 months. EOT and EOS may be the same visit if subject is discontinuing

the study drugs and is not going into LTFU. 9 Heart rate, blood pressure, temperature, respirations.

¹⁰ Hematology and chemistry must be done prior to ublitaximab administration.

¹¹ See Section 8.5.3: Guidelines for Administration of Venetoclax for dose ramp-up schedule and recommended blood chemistry monitoring based on tumor burden.

¹² Cycle 4, day 8, 15 and 22 only required for patients receiving venetoclax and during the venetoclax ramp-up.
13 PT/INR to be done at screening and as clinically indicated. INR should be monitored closely in subjects receiving venetoclax and warfarin.

¹⁴ Serum virology to include HBsAg, HBcAb and HCV AB. If HBcAb is positive subjects must be evaluated for the presence of active HBV by PCR. If HCV AB positive, subjects must be evaluated for the presence of HCV by

¹⁵ At baseline, CMV IgG and IgM or CMV by PCR (if institutions SOC). Thereafter, CMV by PCR for all subjects while receiving umbralisib beginning C4D1, then C6D1 and approximately every 3 cycles thereafter up to Cycle

^{24,} then approximately every 6 cycles thereafter. If CMV IgM or IgG is positive, subjects must be evaluated for the presence of active CMV by PCR U2-VEN-207

	_		_			_		_	_	_		_	_				
E0S,8														X			X
LTFU7											X			X			
30-and 90-Day Safety FU ⁶																×	
EOT																×	×
Cycle 18 and Q3 Cycle ⁵	D1	C24									C24			X25		X	X
Cycles 9, 12, 15s	D1	C12			X						C12 and C15		C12	X25		X	X
Cycles 5&6 ³	D1				X						90		90			×	X
	D22															×	
Cycle 44	D15															×	
Cyc	8Q															×	
	D1				X							X		X	×	×	X
Cycles 2-33	D1				X								E)			X	X
	D15												X			×	X
Cycle 1 ²	8Q															×	X
Č	D2															×	X
	D1												X			×	X
Screening ¹	D-30 to D0	X	X	X		X19		X	X^{20}	X	X			X	X	×	
Cycle = 28 days	Procedure/Days	Quant IgG, IgA, IgM16	β ₂ -microglobulin	Serum Pregnancy Test ¹⁷	Urine Pregnancy ¹⁸	BM	biopsy/aspirate	EKG	AH9I	FISH and NGS ²¹	MRD ²²	Sparse PK ²³	Immunogenicity ²⁴	Response Assessment ²⁵	TLS Risk- Assessment ²⁶	AE Assessment ²⁷	Con Med Assessment

¹⁶ To be completed at baseline, during Cycle 12, and during Cycle 24 only.

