7.1 LOCAL LABORATORY ASSESSMENTS

1. Hematologic profile and serum chemistry to include:

TABLE 6. HEMATOLOGIC INDICES AND SERUM CHEMISTRY TO BE PERFORMED LOCALLY

Hema	tologic Profile	
Hematocrit	Neutrophils	Platelet count
Hemoglobin	Lymphocytes	
Erythrocyte count	Monocytes	
Leukocyte count	Eosinophils	
Absolute neutrophil count	Basophils	
Comp	m Chemistry	
Seru		
A 11	_	CCOT [ACT]
Albumin	Creatinine	SGOT [AST]
Albumin Alkaline phosphatase	_	SGOT [AST] SGPT [ALT]
	Creatinine	
Alkaline phosphatase	Creatinine Glucose	SGPT [ALT] Sodium
Alkaline phosphatase Bicarbonate/CO ₂	Creatinine Glucose LDH	SGPT [ALT]

- 2. Quantitative Immunoglobulins (IgG, IgA, IgM)
- 3. Serum β-HCG test for women of child-bearing potential
- 4. Urine pregnancy test for women of child-bearing potential (Phase 3 patients only)
- 5. Coagulation lab tests to include PT and INR
- 6. β2-microglobulin
- 7. Serum virology to include HBsAg, HBcAb, HCV AB, CMV IgG and CMV IgM (site may perform CMV by PCR if that is their SOC). If HBcAb, HCV AB or CMV IgM or IgG is positive, subjects must be evaluated for the presence of active HBV, HCV, or CMV by PCR
- 8. Coombs test (Coombs test not required in subjects enrolled to V3.0 or later)
- 9. BM aspirate/biopsy. (BM for morphology by local laboratory to confirm CR, BM aspirate for MRD assessment to be analyzed at the central laboratory)
- 10. TLS Risk-Assessment as per venetoclax package insert. C4 pre dose labs include CMP, Mg, Phosphorus, uric acid and LDH. Venetoclax post dose ramp up labs include potassium, uric acid, phosphorus, calcium and creatinine.
- 11. IGHV mutation status
- 12. CMV by PCR

[figure not shown]

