8.5.4 DOSE HOLD/MODIFICATION: UBLITUXIMAB, UMBRALISIB AND VENETOCLAX

Table 22 illustrates the dose hold and modifications for all investigational products in the present study.

Subjects should be assessed clinically for toxicity at each visit using the NCI CTCAE v5.0 (https://ctep.cancer.gov/protocoldevelopment/electronic_applications/docs/ctcae_v5_quick_reference_5x7.pdf) grading scale.

Dose hold and/or modification guidance is for adverse events considered *related* to the study drug(s). If the adverse event is *not considered related* to a study drug (ublituximab, umbralisib and/or venetoclax), then that drug does not need to be modified or held as per Investigator assessment.

If cytopenias are deemed related to the underlying disease rather than study drug, dose modifications are not required, or are per investigator discretion. If a subject discontinues one or more study drugs, the subject may continue treatment with the other study drug(s) per the protocol.

U2-VEN-207

Dose reduction and/or holds are permitted as per Investigator discretion to manage adverse events related to one or more of the study drugs. The guidelines below are recommendations and are not meant to replace Investigator discretion.

TABLE 22. STUDY DRUG MODIFICATIONS

	Ublituximab	Umbralisib	Venetoclax	
NCI CTCAE Grade				
Neutropenia				
Grade 1-2 neutropenia	Maintain full dose. Consider growth- factor support as warranted.	Maintain current dose. Consider growth-factor support as warranted.	Maintain current dose. Consider growth-factor support as warranted.	
Grade 3 neutropenia	Maintain full dose. For recurrent or persistent Grade 3 neutropenia hold ublituximab until Grade ≤2, then resume. Consider growth- factor support as warranted.	Maintain current dose. If recurrence or persistent Grade 3, hold umbralisib until Grade ≤ 2 and resume at same dose. Consider growth-factor support as warranted.	Maintain current dose, if Grade 3 recurs or is persistent then hold venetoclax until ≤ Grade 2, after resume at the same dose. Consider growth-factor support as warranted.	

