Grade 4 neutropenia or occurrence of Neutropenic fever or infection	Hold ublituximab until Grade ≤ 3 and/or neutropenic fever or infection is resolved; consider growth factor support as warranted; thereafter, resume at full dose	Hold umbralisib until Grade ≤3 and/or neutropenic fever or infection is resolved; thereafter, resume umbralisib at current dose. Consider growth- factor support as warranted. If recurrence after rechallenge despite maximum supportive care, hold umbralisib until ≤ Grade 3; thereafter resume umbralisib at next lower dose level.	Hold venetoclax until Grade ≤3 and/or neutropenic fever or infection is resolved; thereafter, resume venetoclax at current dose. Consider growth- factor support as warranted. If recurrence after rechallenge despite maximum supportive care, hold venetoclax until ≤ Grade 3; thereafter resume venetoclax at next lower dose level.	
Thrombocytopenia				

U2-VEN-207

	Ublituximab	Umbralisib	Venetoclax	
	Ublituximab	Umbralisib	Venetoclax	
Grade 3 thrombocytopenia	Maintain full dose.	Maintain current dose.	Maintain current dose.	
Grade 4 thrombocytopenia	Hold ublituximab until Grade ≤ 3; thereafter resume at full dose.	Hold umbralisib until Grade ≤3; thereafter, resume umbralisib at current dose. If recurrence after rechallenge despite maximum supportive care, hold umbralisib until ≤ Grade 3; thereafter resume umbralisib at next lower dose level.	Hold venetoclax until Grade ≤3; thereafter, resume venetoclax at current dose. If recurrence after rechallenge despite maximum supportive care, hold venetoclax until ≤ Grade 3; thereafter resume venetoclax at next lower dose level.	
Infection (including opportunistic infection)				
	Ublituximab	Umbralisib	Venetoclax	
Grade 2 infection	Consider dose hold and/or supportive care as per investigator discretion.	Consider dose hold and/or supportive care as per investigator discretion.	Consider dose hold and/or supportive care as per investigator discretion.	
Grade 3 or 4 infection	Withhold ublituximab until resolved, then resume at full dose.	Withhold umbralisib until resolved, then resume at same or reduced dose.	Withhold venetoclax until resolved, then resume at same or reduced dose.	

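### Arm A has no scheduled blood count on Cycle 4 Days 8, 15 and 22, when chemistry is already drawn and venetoclax rises to 50, 100 and 200 mg; adding one is a cheap improvement

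*Combined protocol and SAP*

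**What the plan says.** Section 6 presents Table 5 as the full list of assessments required in Phase 3, and Section 7 refers laboratory timing back to the assessment tables. A blank cell therefore means that the test is not scheduled.

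The Cycle 4 columns carry the footnote "Cycle 4 Day 8, 15, and 22 visits only for subject randomized to Arm A (U2-V). Study visits have a±3 day window". On those three days the table marks vital signs, chemistry and adverse event assessment. The chemistry row has its own note: "Cycle 4, day 8, 15 and 22 only required for patients receiving venetoclax and during the venetoclax ramp-up". The hematology row is empty on these days and marked on Cycle 4 Day 1 and on Day 1 of Cycles 5 and 6. Its footnote is "Hematology and chemistry must be done prior to ublitaximab administration", and Table 10 (Section 8.3) gives ublituximab once in Cycle 4, on Day 1.

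Section 7.1 item 10 describes the blood tests that follow each ramp-up dose: "Venetoclax post dose ramp up labs include potassium, uric acid, phosphorus, calcium and creatinine". Table 19 (Section 8.5.3.1) monitors the same five chemistries.

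Table 22 (Section 8.5.4) sets hold rules by laboratory grade. For Grade 3 neutropenia the venetoclax column says "Maintain current dose, if Grade 3 recurs or is persistent then hold venetoclax until ≤ Grade 2, after resume at the same dose" and the umbralisib column "If recurrence or persistent Grade 3, hold umbralisib until Grade ≤ 2 and resume at same dose". For Grade 4 neutropenia the venetoclax rule is "Hold venetoclax until Grade ≤3 and/or neutropenic fever or infection is resolved", and umbralisib is treated alike. Grade 4 thrombocytopenia also holds both oral drugs. The section introduces the table with this caution: "The guidelines below are recommendations and are not meant to replace Investigator discretion".

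**The concern.** The hold rules depend on neutrophil and platelet grades, and a cytopenia without symptoms shows only on a count. Cycle 4 is the cycle in which a new drug is started and raised every week, yet its three mid-cycle draws are limited to chemistry.

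The protocol itself expects cytopenia. Section 1.5 reports Grade 3/4 neutropenia in 41% of patients in the venetoclax Phase 1 study. Section 1.6 reports Grade 3 or higher neutropenia in 21% of 43 patients on U2-V. Section 3.1 admits subjects with neutrophils of 750 and platelets of 40,000 per microliter.

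If a qualifying cytopenia arises after Day 1 without symptoms and nobody orders a count, both oral drugs continue and venetoclax keeps rising until the next scheduled count. If it recovers before Cycle 5 Day 1, the schedule never records it.

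**Working it through.** The plan states no figure to reproduce. The check is the Table 5 marks set against the venetoclax doses in Table 10, followed by interval arithmetic.

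| Visit | Venetoclax dose starting | Chemistry | Hematology |
|---|---|---|---|
| Cycle 4 Day 1 | 20 mg | yes | yes |
| Cycle 4 Day 8 | 50 mg | yes | no |
| Cycle 4 Day 15 | 100 mg | yes | no |
| Cycle 4 Day 22 | 200 mg | yes | no |
| Cycle 5 Day 1 | 400 mg | yes | yes |

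Three of the four dose increases (to 50, 100 and 200 mg) therefore have no scheduled count. The column alignment can be checked against Cycle 1 Day 15, where vital signs, hematology and chemistry are all marked in the same row positions.

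Inputs: a 28-day cycle and a window of ±3 days on Cycle 4 and Cycle 5 visits (Table 5 footnotes); 200 and 150 planned subjects per arm in the treatment naïve and previously treated cohorts (Section 4.1).

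- Gap between scheduled counts now: 28 days. With windows: 28 − 3 − 3 = 22 to 28 + 3 + 3 = 34 days.
- Wait for an event that starts on a given day, counting Cycle 5 Day 1 as Day 29: Day 8, 29 − 8 = 21 days; Day 15, 29 − 15 = 14 days; Day 22, 29 − 22 = 7 days.
- Gap if Days 8, 15 and 22 carry a count: 7 days. With windows: 7 − 6 = 1 to 7 + 6 = 13 days.
- Extra counts at full enrollment with the standard ramp-up: 3 × 200 = 600 and 3 × 150 = 450, together 1,050.

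No ublituximab dose falls between the two counts, so only the umbralisib and venetoclax holds are affected. A first Grade 3 neutropenia and a Grade 3 thrombocytopenia call for no hold and are outside the point.

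I give no percentage of events detected. Such a figure would need the timing and duration of cytopenia in Cycle 4, and the documents give neither. Assuming even onset would only restate the 28-day and 7-day intervals.

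**The case against.** The case on the other side has several parts.

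First, a reader might infer that the Table 22 holds cannot operate during ramp-up. The documents do not support that. A Grade 4 cytopenia on Cycle 4 Day 1 or Cycle 5 Day 1 is found by schedule, and so is a Grade 3 neutropenia that persists from Cycle 3 Day 1 to Cycle 4 Day 1. What remains is the interval between the two Cycle 4 and Cycle 5 counts.

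Second, 28 days is the ordinary interval between counts in Cycles 2 to 6. The step from Cycle 6 Day 1 to Cycle 9 Day 1 is longer still (3 × 28 = 84 days), at 400 mg, and the documents do not show that cytopenia clusters in the ramp-up. This stands: the interval is not out of line with the rest of the schedule. Cycle 4 is singled out because the dose rises weekly and blood is already being taken. Closing the later gap would need new visits.

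Third, sites may order counts, toxicity is assessed clinically at each visit, temperature is taken, and neutropenic fever or infection triggers a hold by itself. Table 22 is advisory, and the venetoclax prescribing information, not available here, may call for counts. All of this limits the practical gap, but none of it schedules a test for the protocol's own thresholds. Section 8.5.2.2 strongly urges sites to follow the hold criteria. For neutropenia and thrombocytopenia, Table 22 gives its own venetoclax rules, whereas for diarrhea and colitis it defers to the label.

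Fourth, counts in Arm A only would raise detection of cytopenia in that arm, in adverse events and dose modifications as well as in laboratory grades. This is a real cost, and the fix has to deal with it.

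**Conclusion.** The point holds in a limited form. For Arm A, a Grade 4 neutropenia or thrombocytopenia, or a recurrent or persistent Grade 3 neutropenia, that first appears after Cycle 4 Day 1 and is asymptomatic would not be found by schedule for up to 28 days, or 34 with windows. This is a cheap safety improvement to a schedule that follows a consistent rule; the schedule is not in breach of the plan.

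The conclusion assumes that the blank hematology cells in Table 5 are as intended and that no other required source supplies a count. The Phase 2 schedule (Table 4) shows the same blanks. It is weak support, because it also shows no chemistry on Cycle 4 Day 1 although its own footnote requires chemistry before ublituximab.

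The benefit in number of subjects cannot be sized. A reader might apply the 21% and 41% rates to the 350 planned Arm A subjects, giving 73.5 and 143.5, and take these as delayed holds. The documents do not support that: the rates cover Grade 3 and above at any time, and nothing says how many cases would be Grade 4 or recurrent, fall in Cycle 4, or be asymptomatic.

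**What to change.** Mark hematology for Arm A on Cycle 4 Days 8, 15 and 22 in Table 5. Add a blood count to the ramp-up labs in Section 7.1 item 10, to be repeated at each ramp-up step if the ramp-up is prolonged, since Table 21 lets a reduced dose run for a further week.

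In Section 11.9 or the SAP, state that the by-arm summary of maximum hematology grade will also be shown without these counts. State also that cytopenia adverse events and dose modifications triggered only by them will be flagged, so that the arms can be compared with and without the added ascertainment.

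The cost is three table cells, one line in Section 7.1, a short addition to the safety analysis, and a way to record the trigger. It adds about 1,050 counts at existing draws (more if ramp-ups are prolonged) and no visits. More cytopenia will be detected in Arm A than in Arm B, and some extra holds during ramp-up may follow; their number cannot be estimated from the documents.
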